4.5 INSTRUCTIONS FOR USE

Instructions for Use are provided with each TearCare System.

4.6 TRAINING

Prior to the start of the study, investigators and study staff who have not been previously trained in the proper use of the TearCare System will be trained in its use. While most investigators should have experience in performing manual expression of the meibomian glands, which is a standard procedure for dry eye patients, investigators will be trained in the protocol method for performing meibomian gland expression using the Clearance Assistant device. All study staff will receive training on the protocol and execution of the study according to applicable regulations and Good Clinical Practices.

5 PRIOR INVESTIGATIONS

5.1 PRECLINICAL TESTING

The TearCare System has been tested extensively on the bench and in clinical validation testing to demonstrate that it meets all specified safety and performance requirements. The following testing and analyses was performed:

- Thermal Requirements: Bench testing was performed to demonstrate that the TearCare System meets the operational temperature requirements (range 41-45°C). Clinical validation testing was also performed to measure the temperature at the inner and outer surfaces of the eyelid during operation of the System and at the surface of the cornea immediately following the treatment. The testing confirmed that the system meets temperature-related performance and safety specifications. No adverse events were observed.
- Software Functionality: Testing was performed to demonstrate that the software in the TearCare SmartHub and SmartLid Devices meet all software design requirements.
- Electrical Safety: Testing was performed to demonstrate that the System meets the electrical safety requirements specified in IEC 60601-1.
- Electromagnetic Compatibility: Testing was performed to demonstrate that the System meets the electromagnetic requirements specified in IEC 60601-1-2.
- Biocompatibility: All patient-contacting materials were reviewed to confirm that they are biocompatible for short-term (<24 hours), skin contact.
- Mechanical Strength: Testing was performed to demonstrate that the system meets mechanical strength requirements.
- Shipping, Storage, and Shelf-Life Testing: Testing was performed to demonstrate that the TearCare System continues to function properly after being exposed to

environmental and shipping conditions specified in ASTM D4169. In addition, accelerated aging testing was performed to demonstrate the SmartLid devices have a minimum shelf life of 6 months.

5.2 PREVIOUS CLINICAL EXPERIENCE

The TearCare System has been studied in two pilot studies. The first study was conducted in 2013 as an Investigator-sponsored study with a prototype version of the TearCare System. The second study was initiated in 2017 with a commercial version of the TearCare System (Sight Sciences protocol #05429). These two studies are summarized below.

5.2.1 CLINICAL STUDY OF THE PROTOTYPE TEARCARE SYSTEM (2013)

A prototype version of the TearCare System was tested in a single center, prospective, randomized study. The study enrolled 18 subjects who were randomized to two treatment arms: (a) Prototype TearCare System, or (b) warm compress treatment. Subjects randomized to the TearCare arm (n=10 subjects) received one, 10-minute session with the prototype device followed by manual expression of the meibomian glands. Subjects randomized to the warm compress arm (n=8 subjects) received standard warm compress therapy (Fire & Ice Mask, Rhein Medical, Inc.) for 5 minutes per day for 2 weeks. Subjects were followed for 4 weeks, with follow-up visits at 1 day, 2 weeks, and 4 weeks.

No adverse events were reported in this study. Table 1 presents the effectiveness outcomes from this study.

This study demonstrated the safety of the TearCare System and provided evidence that TearCare System provides statistically significant improvement in meibomian gland secretion, tear break-up time, and dry eye symptoms. Results from this study informed the decision to continue development on the TearCare System.

Table 1: Prototype TearCare System - Study Results (2013)

	TearCare (n=10 subjects, 20 eyes)			Warm Compress control (n=8 subjects, 16 eyes)		
	Baseline	4 weeks	Change BL to 4 wks – p value	Baseline	4 weeks	Change BL to 4 wks – p value
Tear Break-up Time (sec) – Mean (SD)	4.6 (0.8)	16.8 (3.1)	<0.0001	4.1 (1.1)	4.6 (1.8)	0.27
Dry Eye Symptom Questionnaires						
Total OSDI Score (0 to 100)	37.0 (17.5)	19.6 (9.9)	0.01	27.8 (23.3)	34.3 (22.6)	0.21
Total SPEED Score (0 to 28)	13.8 (2.7)	7.4 (4.0)	0.001	13.6 (6.0)	10.1 (6.7)	0.19
Meibomian Gland Assessment						
Total Meibomian Gland Score (0 to 45)	13.4 (7.4)	43.2 (1.4)	<0.0001	7.6 (4.5)	15.4 (7.7)	0.03
# Glands Secreting Any Liquid (0 to 15)	3.6 (3.6)	14.9 (0.3)	<0.0001	1.1 (1.1)	4.4 (3.8)	0.04
# Glands Yield Clear Liquid (0 to 15)	0.3 (0.7)	12.9 (1.8)	<0.0001	0 (0)	1.25 (1.8)	0.08

5.2.2 CLINICAL STUDY OF THE TEARCARE SYSTEM (2017)

Following completion of the design and development of the commercial version of the TearCare System, a single center pilot study was initiated to collect additional clinical data. The results from this study were published in Clinical Ophthalmology.³⁸

Objectives

The objective of this study was to evaluate the clinical utility, safety, and effectiveness of the TearCare™ System compared to standardized warm compress therapy.

Subjects

Twenty-four (24) subjects with symptoms of dry eye in the past 3 months were enrolled. The average age was 67.6 ± 13.5 years (range 29.7 – 89.8 years). All subjects were female, white and not Hispanic or Latino. All subjects had a SPEED score ≥ 6 at the Baseline visit. All subjects had a Tear Break-up Time (TBUT) of <10 seconds in at least one eye at baseline and 72% (17/24) had a Schirmer 1 score (non-anesthetized) of ≤ 10 mm in at least one eye at the Baseline visit.

Methods

This was a prospective, single-center, randomized, parallel-group, clinical trial. Subjects with DED were randomized to either a single TearCare treatment conducted at the clinic or 4 weeks of daily warm compress therapy. The TearCare procedure consisted of 12 minutes of thermal eyelid treatment immediately followed by manual expression of the meibomian glands. Warm compress therapy consisted of once daily application of the compresses to the eyelids for 5 minutes. Subjects were followed to 6 months post-treatment. The primary effectiveness endpoint was defined as change from baseline to

³⁸ Badawi D. A novel system, TearCare®, for the treatment of the signs and symptoms of dry eye disease. Clinical Ophthalmology 2018;12: 683-694.

4 weeks for Tear Break-up Time (TBUT). Secondary effectiveness endpoints included meibomian gland assessment, corneal and conjunctival staining scores, and assessment of dry eye symptoms using validated questionnaires. Safety was evaluated by collecting device-related adverse events, intraocular pressure, and best spectacle-corrected Snellen Visual acuity.

Results

Twenty-four subjects were enrolled and completed 6 months follow-up. Data are summarized in Table 2 below.

At 1 month follow-up, TearCare subjects demonstrated an improvement from baseline in mean (\pm SD) TBUT of 11.7 ± 2.6 seconds compared with an average worsening of -0.3 ± 1.1 seconds for subjects in the warm compress group ($p<0.0001$). Significantly greater improvements in the change from baseline in meibomian gland scores, as well as corneal and conjunctival staining scores were observed in the TearCare group. Subjects in the TearCare group also showed significantly greater improvement in dry eye symptoms as measured by the three questionnaires.

No adverse events were reported in either group.

Table 2: TearCare System – Pilot Study Results (2017)

	TearCare (n=24 eyes, 12 subjects)			Warm Compress control (n=24 eyes, 12 subjects)		
	Baseline	4 weeks	6 months	Baseline	4 weeks	6 months
Tear Break-up Time (sec) – Mean (SD)	3.1 (0.8)	14.8 (2.6)	7.9 (1.5)	3.3 (1.0)	3.1 (0.8)	3.0 (1.0)
Dry Eye Symptom Questionnaires						
Total OSDI Score (0 to 100)	41.0 (18.4)	15.7 (12.2)	30.3 (15.1)	33.0 (19.9)	24.6 (15.2)	30.3 (15.1)
Total SPEED Score (0 to 28)	15.7 (5.2)	7.8 (3.5)	8.2 (6.0)	14.4 (3.8)	12.6 (3.3)	12.2 (4.0)
Total SANDE Score	64.9 (25.9)	40.2 (18.8)	45.9 (30.5)	55.9 (31.5)	57.5 (25.7)	62.1 (21.8)
Meibomian Gland Assessment						
Total Meibomian Gland Score (0 to 45)	6.3 (3.6)	41.0 (2.1)	31.5 (5.5)	9.0 (4.3)	8.2 (4.0)	9.4 (3.5)
# Glands Secreting Any Liquid (0 to 15)	0.8 (0.9)	14.6 (0.8)	11.5 (2.4)	1.3 (1.7)	1.3 (1.6)	1.7 (1.5)
# Glands Yield Clear Liquid (0 to 15)	0.0 (0.0)	11.4 (1.6)	5.4 (3.0)	0.3 (0.7)	0.0 (0.0)	0.1 (0.4)
Corneal Staining Score (0 to 15)	3.5 (1.8)	0.2 (0.4)	3.2 (2.6)	3.4 (2.9)	3.2 (2.6)	3.2 (2.8)
Conjunctival Staining Score (0 to 15)	3.7 (2.5)	0.1 (0.3)	0.3 (0.7)	3.0 (3.4)	4.1 (3.5)	3.2 (3.1)

Conclusions

The TearCare Group consistently showed a significant improvement between the baseline and 4 weeks follow-up for all outcome measures, whereas the Warm Compress group did not. For all outcome measures, the TearCare Group's mean change between baseline and 4 weeks follow-up was better than the Warm Compress group. These results were maintained out to 6 months.

This pilot study provided preliminary evidence of the safety and effectiveness of the TearCare device in relieving the signs and symptoms of dry eye.

5.2.3 SUMMARY

The two prior clinical studies provided preliminary clinical data with the TearCare System. Both of these studies were small, single-center pilot studies.

This current trial is being undertaken to evaluate the safety and efficacy of the TearCare system versus treatment with the LipiFlow System in a prospective, multi-center, hypothesis-driven, randomized, controlled trial. The study is intended to demonstrate that the TearCare System is indicated in the treatment of signs and symptoms of dry eye disease.

6 STUDY ENDPOINTS

6.1 EFFECTIVENESS ENDPOINTS

This study will collect data to assess the impact of each treatment on the signs and symptoms of dry eye disease. Tear Break-Up Time and meibomian gland secretion scores, which measure the treatment effect of the device on the signs of dry eye disease, are the primary endpoints. The Ocular Surface Disease Index (OSDI) questionnaire, which is a validated instrument for measuring the severity of symptoms of dry eye disease, is the key secondary endpoint. The following other secondary endpoints have been chosen to collect additional data regarding changes in the signs and symptoms of dry eye disease in study subjects: Corneal and Conjunctival Staining, the Symptom Assessment iN Dry Eye (SANDE) questionnaire, the Eye Dryness Score, and Meibomian Gland Secretion Score (number of glands yielding clear liquid or any liquid at all).

For each outcome measure, results from the TearCare subjects will be compared with results from the LipiFlow subjects. All the primary and secondary endpoints will be at 1 month.

- **Primary effectiveness endpoints**
 - Mean Change from baseline in Tear Break-Up Time (TBUT)
 - Mean Change in the total Meibomian Gland Secretion Score³⁹

³⁹ Bron AJ, Benjamin L, Snibson GR. Meibomian gland disease. Classification and grading of lid changes. Eye 1991;5: 395–411.

- **Secondary effectiveness endpoints**
 - Mean Change from baseline in OSDI score⁴⁰
 - Mean Change from baseline in corneal staining scores
 - Mean Change from baseline in conjunctival staining scores
 - Mean Change from baseline in SANDE scores^{41,42}
 - Eye Dryness Score
 - Mean Change from baseline in the number of meibomian glands yielding clear liquid secretions
 - Mean Change from baseline in the number of meibomian glands secreting any liquid (clear or cloudy)
- **Additional Exploratory Endpoints**
 - Use of dry eye lubricants

6.2 SAFETY ENDPOINTS

- **Primary Safety Endpoint**
 - Device-related adverse events (all adverse events will be recorded)
- **Secondary Safety Endpoints**
 - Discomfort/pain during treatment
 - Change in best corrected visual acuity (ETDRS)
 - Change in intraocular pressure (IOP)

7 STUDY DESIGN

This is a prospective, randomized, controlled, single-masked, multi-center treatment study. This is a post-market study intended to collect data to update the indication for use for the TearCare System. To reduce potential bias in the study, study staff performing the endpoint assessments will be masked as to the subject's treatment arm. Subjects cannot be masked as it will be obvious to them which treatment they are receiving.

⁴⁰ Schiffman RM, Christianson MD, Jacobsen G, Hirsch JD, Reis BL. Reliability and validity of the Ocular Surface Disease Index. *Arch Ophthalmol* 2000;118: 615-621.

⁴¹ Schaumberg DA, Gulati A, Mathers WD, Clinch T, Lemp MA, Nelson JD, Foulks GN, Dana R. Development and Validation of a Short Global Dry Eye Symptom Index. *Ocular Surface*. 2007;5(1):50-57.

⁴² Amparo F, Schaumberg DA, Dana R. Comparison of Two Questionnaires for Dry Eye Symptom Assessment: The Ocular Surface Disease Index and the Symptom Assessment in Dry Eye. *Ophthalmology*. 2015;122(7):1498-1503.

7.1 STUDY DEVICE AND CONTROL ARM

In this study, treatment with the TearCare System (study device) will be compared with treatment with the LipiFlow System (control arm).

TearCare treatment includes an in-office 15 minute bilateral treatment session with the TearCare System immediately followed by manual expression of the meibomian glands using the Clearance Assistant device. Subjects randomized to TearCare will receive one in-office TearCare treatment on study Day 0.

The LipiFlow System is indicated for use as follows:

The LipiFlow System is intended for the application of localized heat and pressure therapy in adult patients with chronic cystic conditions of the eyelids, including Meibomian Gland Dysfunction (MGD), also known as Evaporative Dry Eye or Lipid Deficiency Dry Eye.

Subjects randomized to LipiFlow will receive the LipiFlow procedure bilaterally conducted per the device instructions for use. The LipiFlow procedure will be performed in-office on study Day 0.

7.2 STUDY CENTERS

This study will be conducted at up to 15 centers in the United States. No center will have more than 20% of the target enrollment (i.e. ≤ 28 subjects per site in Cohort 2).

8 STUDY SELECTION CRITERIA

8.1 INCLUSION CRITERIA

For inclusion in this study, subjects must meet all of the following criteria:

1. At least 22 years of age
2. Reports dry eye symptoms within the past 3 months
3. Reports having to use artificial tears or lubricants regularly over the past month to relieve dry eye symptoms.
4. OSDI Score of 23-79
5. TBUT of ≤ 7 seconds in both eyes
6. Meibomian gland obstruction in both eyes based on a total Meibomian Gland Secretion Score ≤ 12 in each eye.
7. At least 15 glands in each lower eyelid should be expressible, with a sterile cotton swab, at the slit lamp.

8. Best corrected visual acuity of 20/100 or better in both eyes.
9. Willing and able to comply with the study procedures and follow-up
10. Willing and able to provide informed consent
11. English-speaking

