8.2 EXCLUSION CRITERIA

A subject who meets any of the criteria listed below (in either eye) will be excluded from the study:

1. Use of any of the following medications:
 - a) Restasis or Xiidra within 60 days prior to enrollment;
 - b) Antihistamines (oral or topical) within 10 days prior to enrollment;
 - c) Systemic medication(s) (other than anti-histamines) that is known to cause ocular dryness (e.g. diuretics, anti-hypertensives, anti-depressants, hormone therapy) and whose dose of this medication(s) has not been stable within 30 days prior to enrollment. There must be no anticipated adjustments to the dose of these medications for the duration of the trial;
 - d) Accutane (at any time);
 - e) Oral tetracyclines or azithromycin within 30 days prior to enrollment; or
 - f) Topical ophthalmic antibiotics, anti-glaucoma medications, steroids, non-steroidal anti-inflammatory medications within 30 days prior to enrollment.

NOTE: Use of any of the above medications (with the exception of 1c) is not permitted during the 1 month follow-up period.

2. Any of the following dry eye treatments:
 - a) Office-based dry eye treatment (e.g. IPL, thermal pulsation [Lipiflow], etc.) within 12 months prior to enrollment;
 - b) Meibomian gland expression within 6 months prior to enrollment;
 - c) Blephex or debridement within 3 months prior to enrollment is an exclusion;
 - d) Punctal occlusion or punctal plug placement within 30 days prior to enrollment;
 - e) Use of TrueTear device within the past 2 weeks. (Subjects must refrain from using the TrueTear device for the duration of the study.); or
 - f) Any history of meibomian gland probing
3. History of eyelid, conjunctiva or corneal surgery (including refractive surgery) within the past year. In addition, subjects with any history of the following are excluded: chalazion surgery, surgery on the tarsal conjunctiva, radial keratotomy (RK), complicated blepharoplasty, lid reconstruction, or significant complications post-refractive surgery.
4. Contact lens use within the past 2 weeks. (Subjects must refrain from wearing

contact lenses during the 1 month follow-up.)

5. History of Ocular Herpes Simplex or Ocular Herpes Zoster
6. Any active, clinically significant ocular or peri-ocular infection or inflammation
7. Recurrent clinically significant eye inflammation, other than dry eye, within 3 months prior to enrollment

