9.5.2 BASELINE EXAMS, TESTS AND QUESTIONNAIRES

After the subject has signed the informed consent form and agreed to participate in the study, the exams, tests and questionnaires listed in the Baseline column of Table 3 should be performed. Refer to Appendix A for instructions for performing the exams and administering the questionnaires.

At this visit, subjects should undergo the following tests and exams, performed in the order indicated below, to screen them for the study qualification and to record baseline data. Items with an asterisk (*) must be performed by a Masked Assessor (Refer to Section 9.7 for more information on the Masked Assessor).

1. Questionnaires: OSDI, SANDE and Eye Dryness VAS
2. Demographics, medical and ocular history
3. Medication use: ocular and systemic

4. Manifest refraction and ETDRS Best-corrected visual acuity*
5. Slit Lamp Exam*
6. Tear Breakup Time*
7. Corneal Staining*
8. Conjunctival Staining*
9. Schirmer 1 Test
10. Meibomian Gland Secretion Scoring*
11. Intraocular pressure*

If, at any point during the visit the subjects fails to meet a subject selection criterion, then the visit can be terminated. Subjects who fail to meet all the selection criteria will be considered a screen failure and will be withdrawn from the study.

Subjects who fail screening may be re-screened for the study after 60 days. If they are re-enrolled, they should be assigned a new subject ID.

NOTE: Questionnaires and exam data collected on subjects prior to enrollment as part of the routine clinical practice may be used to pre-screen patients for the study. However, once the subject signs the consent form and is enrolled in the study, these questionnaires and exams must be repeated following the protocol procedures.

After all required measurements have been obtained and it has been confirmed that the subject meets all the Subject Selection Criteria, then the subject will be Randomized.

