9.6 FOLLOW-UP VISITS

Prior to the Visit: Reminder Call

A few days before the follow-up visit, it is recommended that the coordinator contact the subject to remind them not to use dry eye drops or lubricants on the day of the follow-up visit since these products can affect the endpoint assessments.

At the Beginning of the Follow-up Visit: Maintaining Masking of Study Personnel

Endpoint assessments performed during the Follow-up visit must be performed by the Masked Assessor (See Section 9.7).

At the beginning of the follow-up visit, the coordinator should remind the subject to not reveal their randomization group to the study personnel who will be performing the follow-up exams.

Order of Procedures During the Follow-Up Visit

Follow-up procedures will be performed per the Study Schedule provided in Table 3 (page 30) and the methods included in Appendix A. Since certain tests/exams can impact the ability to perform other tests/exams, the following tests and exams should be performed in this order:

1. Questionnaires
2. Manifest refraction, if required per this protocol, and ETDRS Best-corrected visual acuity
3. Slit Lamp Exam
4. Tear Breakup Time
5. Corneal staining
6. Conjunctival staining
7. Meibomian Gland Secretion Scoring

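### Baseline gland scoring directly follows a Schirmer test that is not repeated at follow-up, and the swab check required by inclusion 7 has no stated place in the Baseline sequence

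*Combined protocol and SAP*

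**What the plan says.** Section 9.5.2 has the Baseline tests "performed in the order indicated below, to screen them for the study qualification and to record baseline data". The relevant entries are "5. Slit Lamp Exam", then TBUT (6), corneal staining (7), conjunctival staining (8), "9. Schirmer 1 Test", "10. Meibomian Gland Secretion Scoring" and IOP (11).

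Section 21.7 describes Schirmer as a filter strip left in the inferior fornix for 5 minutes without anesthesia. Section 21.8 describes gland scoring as pressing below the lash line of the lower lid and rolling its margin outward, with 15 glands graded 0 to 3.

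Table 3 marks Schirmer at Baseline only. Section 9.6 goes from conjunctival staining straight to gland scoring at follow-up, and gives its reason for fixing the sequence: "Since certain tests/exams can impact the ability to perform other tests/exams, the following tests and exams should be performed in this order".

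Inclusion 7 in 8.1 adds an eligibility check: "At least 15 glands in each lower eyelid should be expressible, with a sterile cotton swab, at the slit lamp". Neither Table 3, nor 9.5.2, nor the slit-lamp method in 21.3 contains a swab step.

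**The concern.** The total gland score is a co-primary endpoint, and the two gland counts from the same examination are secondary endpoints. All three are analyzed as change from baseline. A change score is easiest to interpret when both measurements follow the same preceding steps. Here the Baseline measurement follows a strip in the lower fornix and, depending on the site, swab expression of the same lid. The Week 2 and Month 1 measurements follow neither. If those steps alter what the glands yield minutes later, the reported change contains a procedural component as well as the effect of treatment.

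The same Baseline score is used for eligibility (12 or less in each eye). If the swab check is done first, the TBUT cut of 7 seconds or less is also applied to a value taken after lid manipulation. With up to 15 centers and no stated timing, practice may differ between sites.

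**Working it through.** **1. The two sequences side by side**

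| | Baseline (9.5.2) | Week 2 and Month 1 (9.6) |
|---|---|---|
| Slit lamp | step 5 | step 3 |
| TBUT | step 6 | step 4 |
| Corneal staining | step 7 | step 5 |
| Conjunctival staining | step 8 | step 6 |
| Schirmer | step 9 | not done |
| Gland scoring | step 10 | step 7 |
| IOP | step 11 | step 8 |
| Swab check (inclusion 7) | required, timing not stated | not listed |

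The Schirmer difference is certain on the text. It reaches gland scoring only, because baseline TBUT is taken before Schirmer. The swab difference is conditional. It reaches TBUT and gland scoring if the check is done at step 5, and neither if it is done after step 10.

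**2. Is the swab check likely to be more than a light touch?** Inclusion 6 requires a total of at most 12 over 15 glands graded 0 to 3. At most 12 glands can then have grade 1 or more, so at least 15 − 12 = 3 graded glands give nothing with the Evaluator. The same lid must show at least 15 glands expressible by swab. Unless ungraded glands make up the number, the swab has to express glands that the Evaluator did not.

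**3. Effect on the primary contrast.** Let the Baseline steps add a common shift s to every baseline score B, so that B′ = B + s. The observed change is y′ = y − s. Putting B = B′ − s into the SAP model (22.1.1) gives

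y′ = (β0 − s − β2·s) + β1·T + β2·B′ + b + ε.

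The shift goes into the intercept and β1 is unchanged. Baseline precedes randomization, so a shift that varies between subjects is also unrelated to arm on average.

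**4. Effect on a within-arm change.** The mean change in each arm moves by −s. The documents give no value for s. To show scale only:

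- Inputs from 22.3.2 and 22.3.4: SD of change 9.0, variance components 15.93 and 20.11, 10% loss, 69 subjects per arm.
- Check of the plan's own figures: design effect 1 + 15.93/(15.93 + 20.11) = 1.44, as stated. 142 × 1.5 = 213 eyes and 213/0.9 = 236.7, stated as 237 eyes; 118.3 subjects, stated as 119. These figures reproduce and are not in dispute.
- Effective eyes per arm: 2 × 69 × 0.9/1.44 = 86.25.
- Standard error of a within-arm mean change: 9/√86.25 = 0.97 units.
- Assumed shift of 1 to 3 units (one to three graded glands moved by one grade): 1/0.97 = 1.0 to 3/0.97 = 3.1 standard errors, or 11% to 33% of the 9-unit change assumed in 22.3.2.

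**5. Effect on eligibility.** With shift s, the cut of 12 acts as a cut of 12 − s on the score that would have been seen without the extra steps. If s is −1 to −3, the effective cut is 13 to 15. If s is +1 to +3, it is 11 to 9. Expression could empty glands (lower Baseline) or clear plugs (higher Baseline), so the sign is unknown.

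**The case against.** Several objections carry weight.

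- *No documented mechanism.* Nothing in the documents says that a strip in the fornix changes gland output, and scoring presses a different surface of the lid. This stands: the size could be nil. Against it, the plan fixes its follow-up order on the ground that tests can interfere with one another.
- *Swab timing is open.* TBUT and corneal staining also use the slit lamp, 21.3 describes inspection only, and 9.5.2 confirms eligibility after all measurements are complete. This stands: the text does not show that the check comes at step 5, so the TBUT point remains conditional.
- *Follow-up lids are not untouched.* Month 1 scoring also follows two dyes placed in the lower fornix and two staining exams. This stands, but those steps occur at Baseline too. Only Schirmer, and possibly the swab check, differ.
- *The gland-count tests are hard to overturn.* The counts are sixth and seventh in the sequence in 12.5.6. In the 2017 pilot's TearCare arm they rose from 0.8 to 14.6 (any liquid) and from 0.0 to 11.4 (clear liquid). If this trial resembles the pilot, a reversed result against 0 is unlikely, and the reported size of change is the more exposed quantity.
- *Within-arm change is already hard to interpret,* because entry requires a low score. This is true, but it is no reason to add another avoidable component.

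A reader might also infer a contradiction between "Meibomian gland expression within 6 months prior to enrollment" in 8.2 and "Subjects who fail screening may be re-screened for the study after 60 days" in 9.5.2 for anyone who has already had the swab check. The documents do not support this. Exclusion 2b sits in a list of dry eye treatments, while the swab check is a diagnostic eligibility test, and exclusion 11 uses swab or digital expressibility in the same diagnostic way.

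**Conclusion.** The point holds in a limited form. It is certain that the total gland score and both gland counts follow a Schirmer test at Baseline and not at Week 2 or Month 1. It is also certain that a required swab check has no stated place in the sequence. It is conditional that the swab check precedes baseline TBUT or gland scoring.

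The non-inferiority comparison is not biased on average. A reader might set an assumed shift beside the 5-unit margin and conclude that the primary test is at risk. That comparison is not valid, because the margin applies to the arm difference and a common shift cancels there. The exposed quantities are the reported within-arm changes, the gland-count tests of change against 0, and the eligibility cut of 12 or less. The TBUT cut and within-arm TBUT change join them only if the swab check comes first.

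The figure of 1.0 to 3.1 standard errors rests on an assumed shift of 1 to 3 units and on the plan's own SD and design effect. It shows that a small shift would be visible in a within-arm mean. It does not show that a shift exists. The change is worth making because it is cheap and removes the question.

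**What to change.** - In 9.5.2, place gland scoring directly after conjunctival staining, as in 9.6. Then add the inclusion 7 swab check as a numbered step, followed by Schirmer and then IOP.
- Align Table 3: add a Baseline-only row for the swab check, and list Schirmer after gland scoring. State in Appendix A how and when the check is done.
- Record the date on which each site adopts the new order, so that the report can say which subjects were measured under which sequence.

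Cost: a revised Baseline worksheet and brief site training, with no change to visits, model or sample size. Schirmer would then follow lid manipulation, which may affect its reading, but it is neither an endpoint nor an eligibility criterion. Section 4.4 shows that the study was already under way, so subjects already enrolled keep the old order and Cohort 2 may contain both. Randomization is expected to balance that mix between arms.
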